## 6. STATISTICAL CONSIDERATIONS

### 6.1 Study Endpoints

#### 6.1.1 Safety Endpoints

Safety endpoints will include:

- Incidence of any local and systemic treatment emergent AEs (TEAEs).
- Number of subjects with presence (and severity) of each individual LSR (telangiectasia, skin atrophy, striae rubrae, erythema, edema, scaling/dryness, stinging/burning, and pruritus) for each treatment area, as applicable, at each time point collected (Baseline, and LTF-Months 1, 3, 6 and 9, and any Unscheduled Visits).
- UPT results in all WOCBP at Baseline, LTF-Month 6 and EOS.

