### 6.3 Sample Size Calculations

For large samples, the two-sided confidence interval for a single proportion extends a distance

$$\omega = z_{1-\frac{\alpha}{2}} \sqrt{\frac{\pi(1-\pi)}{n}}$$

from the observed proportion in both directions.

An incidence no greater than 1% of important AEs out of 100 subjects will provide the estimate of no greater than a 3% prevalence of important AEs at the 95% confidence level with a much larger number of subjects exposed for the same duration (i.e., 12 months). Applying the same approach, an incidence no greater than 1% of important AEs out of 300 subjects will provide the estimate of no greater than a 2.1% prevalence of important AEs at the 95% confidence level with a much larger number of subjects exposed for the same duration (i.e., 6 months).

Approximately six hundred (600) subjects had to be enrolled in order to have 300 subjects on-study at 6 months and 100 subjects on-study at 12 months. These treatment durations include the 0 or 3 months of active treatment in the Phase 3 pivotal studies (CB-03-01/25 and CB-03-01/26).

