### 7.1 Tables, Listings and Figures layout

Tables and Listings will be provided according to the following settings:

- Background: White
- Foreground: Black
- Font face: Times
- Font style: Roman
- Font size: 10 pt
- Font weight: Medium (data, footers and notes), Bold (titles and headers)
- Font width: Normal
- Layout: Landscape
- Top Margin: 0.8 cm
- Bottom Margin: 0.8 cm
- Left Margin: 0.8 cm
- Right Margin: 0.8 cm
- Test label: CB-03-01
- Date format: ddMMMyyyy
- Means, standard deviations, percent coefficient of variations, medians, lower confidence limits and upper confidence limits will be rounded to one digit more than the original data
- Minima and maxima will keep the same number of decimal digits as the source values

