### 7.2 Analysis sets

Subjects who completed 6 months or 12 months on-study without material non-compliance with test article (CB-03-01 cream, 1%) dosing per protocol will count towards the desired 300 subjects at 6 months and 100 subjects at 12 months.

The following analysis sets will be defined:

1. Intent-to-Treat Set (ITT): all enrolled subjects. This analysis set will be used for efficacy analyses.
2. Per Protocol Set (PP): all enrolled subjects who completed the study without any significant protocol deviations. This analysis set will be used for efficacy analyses.
3. Safety Set: all subjects who received at least one application of the test article. This analysis set will be used for safety analyses.

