## 7.9 *Safety analysis*

All safety analyses will be performed on subjects of the Safety set. Subjects will be analysed according to the treatment they actually received.

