### 7.9.2 *Adverse events*

All AEs will be coded using the Medical Dictionary for Regulatory Activities (MedDRA) and listed. The version of the dictionary used for coding will be reported in the clinical study report.

Individual TEAEs (i.e. all the all AEs occurring or worsening after the first dose of the test article) will be listed ([Listing 16.2.7.1](#)).

TEAEs will be summarised as follows:

- The number and percentage of subjects with any TEAE and the number of TEAEs will be presented overall ([Table 14.3.1.1](#)) and by SOC and PT ([Table 14.3.1.2](#));
- The number and percentage of subjects with any TEAE by relationship and the number of TEAEs by relationship will be presented ([Table 14.3.1.1](#));
- The number and percentage of subjects with any TEAE related to the IMP and the number of TEAEs related to the IMP will be presented by SOC and PT ([Table 14.3.1.3](#));
- The number and percentage of subjects with any TEAE by severity and the number of TEAEs by severity will be presented overall ([Table 14.3.1.1](#)) and by SOC and PT ([Table 14.3.1.4](#));
- The number and percentage of subjects with any TEAE leading to discontinuation and the number of TEAEs leading to discontinuation will be presented ([Table 14.3.1.1](#)).

Serious TEAEs will be summarised as follows:

- The number and percentage of subjects with any Serious TEAE and the number of Serious TEAEs will be presented overall (Table 14.3.1.1) and by SOC and PT (Table 14.3.1.5);
- The number and percentage of subjects with any Serious TEAE by relationship and the number of Serious TEAEs by relationship will be presented (Table 14.3.1.1);
- The number and percentage of subjects with any Serious TEAE related to the IMP and the number of Serious TEAEs related to the IMP will be presented by SOC and PT (Table 14.3.1.6);
- The number and percentage of subjects with any Serious TEAE leading to discontinuation and the number of Serious TEAEs leading to discontinuation will be presented (Table 14.3.1.1).
- The number and percentage of subjects with any Serious TEAE leading to death and the number of Serious TEAEs leading to death will be presented (Table 14.3.1.1).

All Serious TEAEs will be listed and all TEAEs leading to discontinuation will be listed (Table 14.3.2.1).

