**10. APPENDICES**

Appendix 1. [Section 14 - Tables Shells](#)

Appendix 2. [Section 16.2 - Individual Subject Data Listings Shells](#)

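### SAP 6.3 sizes the study on a 95% limit for undefined important AEs, but the text of SAP 7.9.2 plans no interval, rate or time-specific incidence to match

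*SAP*

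**What the plan says.** SAP 6.3, repeating Protocol 17.1, gives the precision argument: "An incidence no greater than 1% of important AEs out of 100 subjects will provide the estimate of no greater than a 3% prevalence", and in the same way 2.1% from 300 subjects. The first limit refers to 12 months of exposure and the second to 6 months. The clock includes the pivotal studies: "These treatment durations include the 0 or 3 months of active treatment in the Phase 3 pivotal studies". SAP 7.2 says that compliant completers of those durations "will count towards the desired 300 subjects at 6 months and 100 subjects at 12 months".

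The analysis is set out elsewhere. SAP 7.9 states "All safety analyses will be performed on subjects of the Safety set". SAP 7.9.2 then plans: "The number and percentage of subjects with any TEAE and the number of TEAEs will be presented overall". It adds breakdowns by SOC and PT, relationship, severity, seriousness, discontinuation and death. The safety endpoint in SAP 6.1.1 is TEAE incidence, with no time point.

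Confidence limits appear outside SAP 6.3 only in the layout rules of SAP 7.1: "lower confidence limits and upper confidence limits will be rounded to one digit more than the original data". No section assigns a limit to AEs. SAP 7.5.3 counts subjects on-study at 3, 6, 9 and 12 months, and SAP 7.8.2 summarises exposure; neither is linked to AEs.

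**The concern.** Long-term safety is the primary objective and SAP 6.2 plans no hypothesis test, so estimates are all that the study delivers. The sample size rests on an upper limit for one class of event at two durations. The text of the SAP does not define that class, does not attach an interval to any AE figure, and does not evaluate AEs at either duration.

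The crude percentage puts every treated subject in the denominator, however short the follow-up. If subjects leave early, it falls below the risk over the planned nine months. It also pools former-vehicle subjects, who enter with no prior CB-03-01 treatment, with former-active subjects, who enter with three months. A reader who sets the reported percentage beside the limits in SAP 6.3 would be comparing different quantities. Leaving the choice of important AEs until the data are known would also weaken any statement about them.

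**Working it through.** **1. The plan's own figures.** Inputs from SAP 6.3: p = 0.01, two-sided 95%, limit = p + 1.96·√(p(1−p)/n).
- n = 100: 0.01 + 1.96·√(0.0099/100) = 2.95% (stated 3%).
- n = 300: 0.01 + 1.96·√(0.0099/300) = 2.13% (stated 2.1%).

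Both reproduce. With so few events the large-sample formula is optimistic: exact upper limits are 5.4% for 1/100 and 2.9% for 3/300. Any interval that is added should therefore be an exact one where possible.

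**2. The term.** Important AEs occur only in the sample-size text. The nearest wording, important medical event in Protocol 14.2, is one criterion for an SAE and is not linked to it.

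**3. Crude percentage with dropout.** The documents give neither dropout nor hazard, so these are assumptions: constant hazard, true 9-month risk 3%, independent exponential loss of a fraction L by month 9.
- h = −ln(0.97)/9 per month; λ = −ln(1−L)/9.
- Crude = h/(h+λ) × [1 − exp(−9(h+λ))], where the exponential equals 0.97·(1−L).

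| L | Crude | Shortfall against 3% (relative) |
|---|---|---|
| 0% | 3.00% | 0% |
| 10% | 2.85% | 5% |
| 30% | 2.53% | 16% |
| 50% | 2.17% | 28% |

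**4. Against the durations in SAP 6.3.** Under the same hazard the 6-month risk is 1 − 0.97^(6/9) = 2.01% and the 12-month risk is 1 − 0.97^(12/9) = 3.98%. With no loss the crude 3.00% is above the first and 25% below the second. At 30% loss it is 37% below the second (2.53/3.98 = 0.63).

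**5. Pooling of prior exposure.** Assume a 1:1 carry-over of pivotal assignment, no loss, a 12-month risk of 4% since first CB-03-01 dose, and a hazard in months 0–3 that is three times the later hazard h₂. Then 3·(3h₂) + 9h₂ = 18h₂ = −ln(0.96), so h₂ = 0.002268.
- Former vehicle, months 0–9: 1 − exp(−15h₂) = 3.34%.
- Former active, months 3–12: 1 − exp(−9h₂) = 2.02%.
- Pooled: 2.68%.

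With hazard ratios of 1, 2, 3 and 5 the pooled figure is 1.49, 1.16, 1.00 and 0.83 times the 6-month risk. The direction of the mismatch therefore cannot be known in advance.

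**6. What a rate would give.** Take step 3 at 30% loss and assume all 609 enrolled (SAP 2.5) are treated. Subject-time is 609 × 0.321/0.04302 = 4,545 months, or 379 years, with about 15 subjects having an event. The rate is 4.0 per 100 subject-years (exact 95% CI 2.2 to 6.5). The assumed hazard is 0.003384 × 12 = 4.1 per 100, so the dropout bias is gone.

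**The case against.** The strongest reply is that SAP 6.3 explains a sample size and does not define an estimand. That stands. A reader might infer that the plan promises a 6- or 12-month incidence and fails to deliver it. The documents do not say so: the declared endpoint is TEAE incidence without a time point, and SAP 7.9.2 reports that. Nor is the arithmetic in SAP 6.3 wrong by its own formula.

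Second, much is already tabulated. Serious, related and discontinuation-leading TEAEs are natural candidates for important AEs, and disposition, on-study counts and exposure are all summarised. This makes the repair easy, but the SAP does not say which category is meant, and none of these tables is time-specific.

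Third, a reader might infer that no interval is planned anywhere. That goes too far: SAP 7.1 has a rounding rule for confidence limits, and the "Section 14 - Tables Shells" listed in SAP 10 are not visible. The point is limited to the SAP text.

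Fourth, a reader might infer that the start of the TEAE clock is open. It is largely settled: Protocol 14 collects AEs from the first dose of test article, and SAP 1 confines the analysis to study 27 data. A one-line confirmation is enough.

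Fifth, the sizes rest on assumed loss and hazards. At 30% loss the shortfall is 3.00 − 2.53 = 0.47 percentage points, about 3 of 609 subjects, while the 95% half-width for 3% of 609 is 1.96·√(0.03·0.97/609) = 1.35 points. The bias is modest against sampling error, though an interval would at least make that error visible.

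Last, both documents plan no subgroup analysis (Protocol 17.4, SAP 7.7). A split by pivotal assignment departs from that and must be declared.

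**Conclusion.** The concern holds in limited form. The sizing rests on an undefined event class at two exposure durations, and the visible analysis text contains no interval, person-time rate or time-specific incidence. The crude percentage understates the 9-month risk whenever subjects leave early: by 5%, 16% and 28% in relative terms at 10%, 30% and 50% loss, if loss is independent and exponential, the hazard constant and the true risk 3%. It estimates neither the 6- nor the 12-month quantity.

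A reader might take a 6-month figure in former-vehicle subjects as the incidence at 6 months of exposure. The documents do not support that label, because Protocol 6.2 allows treatment of an area to be stopped and restarted; the figure is incidence by time since first dose. The 12-month quantity cannot come from study 27 data alone, since each subject spends nine months in it.

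No planned table is invalid. This is a worthwhile and inexpensive improvement, not a fatal defect.

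**What to change.** Before database lock, keeping the crude tables:

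- **(a)** State which planned TEAE categories count as important AEs, for example serious, related, or leading to discontinuation.
- **(b)** Confirm that the TEAE clock starts at the first dose in study 27.
- **(c)** For those categories add to SAP 7.9.2:
  - an incidence rate, as subjects with an event over subject-time from first LTF dose to first event or study exit, with exact Poisson 95% CI, labelled as follow-up time because it includes periods off treatment;
  - 1 minus Kaplan-Meier cumulative incidence with 95% CI and numbers at risk, at 6 months and one later time, labelled by time since first LTF dose and not by months of exposure.

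  Choose the later time so that most subjects are still followed, including those first dosed after Day 1. Visit 10 may occur from Day 253 (274 − 21), so a subject first dosed at Day 29 may leave 253 − 29 = 224 days after that dose. Do not restrict the denominator to the completers counted in SAP 7.2, which would drop subjects who stop early for an AE.
- **(d)** Show the 6-month figure descriptively by pivotal assignment, as a stated exception to SAP 7.7. If 609 split 1:1 and all start on Day 1, about 284, 240 and 192 per group remain at Day 183 with 10%, 30% and 50% loss by Day 274: 304.5 × (1−L)^(183/274).
- **(e)** State that the 3% limit at 12 months is a planning figure that the study 27 analysis does not estimate, unless pivotal AE records are linked.

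The cost is a few tables, an independent-censoring assumption and one declared exception to the no-subgroup rule. No new data are collected for (a) to (d). Pivotal assignment is already needed for the 12-month count in SAP 7.5.3.

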6.3 Warnings, Precautions and Contraindications

The test article is for topical use only. Care should be taken to avoid contact with eyes and all mucous membranes. If contact with eyes occurs, rinse thoroughly with water.

Subjects with a known sensitivity to any of the ingredients in the test article should not participate in this study.

Should skin irritation or rash develop, subjects should discontinue use and contact the study site.

In case of accidental ingestion, subjects should contact the investigator immediately.

The effects of the test article in nursing mothers, pregnant women and their unborn children are unknown. WOCBP must not be pregnant or planning a pregnancy during the study period.

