13.2 Subject Discontinuation

A subject may be withdrawn from the study prior to completion for any of the following reasons:

- Whenever the subject or the subject's parent/guardian decides it is in the subject's best interest to be withdrawn, Note: if the subject or parent/guardian decides to withdraw from the study due to an AE then it should be classified as withdrawal due to an AE.
- Whenever the investigator decides it is in the subject's best interest to be withdrawn
- AEs
- Worsening of condition or treatment failure (in the opinion of the investigator)
- Noncompliance
- Pregnancy
- Lost to follow-up
- Sponsor administrative reasons

If a subject withdraws prematurely during the nine month treatment period for any reason, the Visit 10 (EOS) procedures should be completed at that time. When a subject is withdrawn from the study for a treatment-related AE (i.e., possibly, probably or definitely related as defined in [Section 14](#)), when possible, the subject should be followed until resolution or stabilization of the AE.

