14. ADVERSE EVENT REPORTING

An **adverse event** (AE) is any untoward medical occurrence associated with the use of a drug in humans, whether or not considered drug related.

An AE (also referred to as an adverse experience) can be any unfavorable and unintended sign (e.g., an abnormal laboratory finding), symptom, or disease temporally associated with the use of a drug, without any judgment about causality. An AE can arise from any use of the drug (e.g., off-label use, use in combination with any drug) and from any route of administration, formulation, or dose, including an overdose.

Information on the medical condition of subjects should begin following the subject's written consent/assent to participate in the study and a medical history should be taken at screening. Other changes in subject health information becomes AE data when the subject begins dosing with the test article and therefore AE data should be collected from the date of the first dose of test article. These data are considered treatment-emergent AEs.

Timely and complete reporting of all AEs assists the contract research organization (CRO) in identifying any untoward medical occurrence, thereby allowing:

- 1) protection of the safety of study subjects;
- 2) a greater understanding of the overall safety profile of the test article;
- 3) recognition of dose-related test article toxicity;
- 4) appropriate modification of study protocols;
- 5) improvements in study design or procedures; and
- 6) adherence to worldwide regulatory requirements.

Test article is defined as a pharmaceutical form of an active ingredient or vehicle/placebo being tested or used as a reference in the study, whether blinded or unblinded. AEs may be either spontaneously reported or elicited during questioning and examination of a subject. All AEs must be completely recorded on the AE CRF. If known, the investigator should report the diagnosis of the underlying illness or disorder, rather than its individual symptoms. Subjects experiencing AEs that cause interruption or discontinuation of test article, or those experiencing AEs that are present at the end of their participation in the study should receive follow-up as appropriate. If possible, report the outcome of any AE that caused permanent discontinuation or that was present at the end of the study particularly if the AE is considered by the investigator to be treatment-related (i.e., definitely, probably, or possibly related to test article).

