Probable - An event that follows a reasonable temporal sequence from administration of the test article; that follows a known or expected response pattern to the test article; and that is confirmed by improvement on stopping or reducing the dosage of the test article; and that is unlikely to have been caused by concurrent/underlying illness or other drugs, procedures, or other causes.

Possible - An event that follows a reasonable temporal sequence from administration of the test article; that follows a known or expected response pattern to the test article; but may have been caused by concurrent/underlying illness, other drug, procedure, or other causes.

Unlikely - An event that does not follow a reasonable temporal sequence from administration of the test article; that does not follow a known or expected response pattern to the test article, or most likely was caused by concurrent/underlying illness, other drug, procedure, or other causes, because of their known effects.

Not Related - An event almost certainly caused by concurrent/underlying illness, other drug, procedure, or other causes.

The investigator should categorize the outcome of the AE according to the following categories:

Fatal - Termination of life as a result of an AE.

Not Recovered/Not Resolved - AE has not improved or the subject has not recuperated.

Recovered/Resolved - AE has improved or the subject has recuperated.

Recovered/Resolved with Sequelae - subject recuperated but retained the pathological conditions resulting from the prior disease or injury.

Recovering/Resolving - AE is improving or the subject is recuperating.

Unknown - Not known, not observed, not recorded or subject refused.

The investigator should report the action taken with the test article due to the AE according to the following categories:

Dose Not Changed - An indication that a medication schedule was maintained.

Dose Increased - An indication that a medication schedule was modified by addition; either by changing the frequency, strength or amount.

Dose Reduced - An indication that a medication schedule was modified by subtraction, either by changing the frequency, strength or amount.

Drug Interrupted - An indication that a medication schedule was modified by temporarily terminating a prescribed regimen of medication.

Drug Withdrawn - An indication that a medication schedule was modified through termination of a prescribed regimen of medication.

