Treatment on the face and/or trunk may be discontinued if/when acne clears (achieves an IGA of grade 0 or "minimal" grade 1) and re-instated if/when acne worsens (IGA \geq 2) according to the assessment of the investigator for each respective treatment area.

If skin irritation or rash develops, subject should discontinue use and contact the study site. In the event that the investigator believes dose modification is necessary due to tolerability issues (e.g., problems with tolerance), the subject's care should be discussed with the Medical Monitor prior to making any dose modifications. All dose modifications must be reported on the appropriate CRF.

A 3.6 Documentation of Application and Compliance

A Subject Diary will be dispensed to the subject to record the dates and times of all application doses and any missed doses of the test article ([Appendix 2](#)). Subjects will be

instructed to bring the diary with them to each study visit. The date and time of the first and last application of the test article will be recorded on the appropriate CRF.

A 3.7 Return and Destruction of Test Article Supplies

Upon completion or termination of the study, all test article tubes must be accounted for and any missing tubes of the test article must be explained on the completed Study Medication Accountability Log. All returned tubes will be weighed to the nearest tenth gram (0.1 gram) in order to document extent of subject exposure. Unless instructed otherwise by the Sponsor, the study site will keep the original Study Medication Accountability Log in the study file. A copy of the Study Medication Accountability Log will be returned to the Sponsor. All tubes of test article will then either be a) returned to the study Sponsor or b) emptied and provided to a sponsor-identified third party vendor for appropriate destruction, according to applicable regulations with the provision of a certificate of destruction.

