### 7.8.3 *Treated areas and dose adjustments*

The treated areas and any dose adjustments will be listed ([Listing 16.2.5.4](#)).

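### By consequence for treatment, the SAP counts only TEAEs leading to an undefined 'discontinuation'; those that interrupted or reduced dosing in subjects who stayed on study get no summary count

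*SAP*

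**What the plan says.** **The SAP's count by treatment consequence.** Section 7.9.2 summarises TEAEs overall and by SOC and PT, relationship and severity, and lists each one. The count tied to treatment is: "The number and percentage of subjects with any TEAE leading to discontinuation and the number of TEAEs leading to discontinuation will be presented". It is repeated for serious TEAEs.

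**The SAP's handling of dose changes.** Section 7.8.3 says: "The treated areas and any dose adjustments will be listed". It cites one listing and no summary table.

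**The protocol on stopping for a reaction.** Section 6.3: "Should skin irritation or rash develop, subjects should discontinue use and contact the study site". Appendix 3, A 3.5 repeats the instruction. It also allows for dose modification for tolerability after discussion with the Medical Monitor, and adds: "All dose modifications must be reported on the appropriate CRF".

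**The protocol on action taken.** Section 14.1 has the investigator record an action for each AE. Dose Reduced, Drug Interrupted and Drug Withdrawn are separate categories, and Drug Interrupted is defined as: "An indication that a medication schedule was modified by temporarily terminating a prescribed regimen of medication".

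**The protocol on leaving the study.** Section 13.2: "A subject may be withdrawn from the study prior to completion for any of the following reasons". AEs are among the reasons. The wording permits withdrawal and does not require it.

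**The concern.** The sole stated objective is the long-term safety of twice-daily use. How many subjects had to withhold or cut back the cream because of an adverse event bears directly on that. Under the SAP text, a subject who stops for a reaction, recovers and resumes is not clearly counted anywhere as having had a dose-limiting event. The report could give a very low figure for TEAEs leading to discontinuation while saying nothing about interruptions.

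The undefined term adds to this. Two programmers could follow section 7.9.2 and count different things: subjects who left the trial, subjects who permanently stopped the cream, or subjects who stopped it for a time.

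**Working it through.** **1. Can a TEAE limit dosing without the subject leaving?** Nothing says so outright, but four provisions together imply it.
- Protocol 6.3 and A 3.5 tell a subject who reacts to stop the cream and contact the site.
- Protocol 13.2 makes withdrawal optional.
- Protocol 14 treats the two outcomes separately when it asks for follow-up of "Subjects experiencing AEs that cause interruption or discontinuation of test article".
- Protocol 14.1 has a category for temporary stops, which would have little use if every stop ended participation.

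**2. Are such events collected?** Yes. Action taken is recorded for each AE. Protocol 10.2, repeated in SAP 3.2, makes a listed LSR an AE when the cream has to be withheld because of it.

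**3. What does discontinuation mean?** SAP 7.5.5 uses it for leaving the trial. Protocol 6.2 and A 3.5 also use it for reversible stops of one area when acne clears. SAP 7.9.2 does not choose. If it means leaving the trial, the count overlaps with withdrawals by reason in SAP 7.5.1. On that reading, or if it means a permanent stop, temporary interruptions and reductions are left out.

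**4. Does another planned summary supply the count?**
- LSR tables (SAP 7.9.1) give severity by visit. Clinic visits fall on Days 29, 85, 183 and 274, so the gaps are 85 − 29 = 56, 183 − 85 = 98 and 274 − 183 = 91 days. An investigator-rated sign that settled in between can be missed unless an unscheduled visit caught it. Stinging/burning and pruritus are rated since the last visit, but without the action taken.
- Compliance (SAP 7.3) divides actual by scheduled applications and does not say whether withheld doses remain scheduled.
- Mean daily amount (SAP 7.8.2) divides by days of treatment, which an interruption may shorten.
- Listing 16.2.5.4 covers all dose adjustments, so stops for clearance are mixed with stops for intolerance unless a reason is shown.

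None of these counts TEAEs leading to interruption or reduction.

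**5. Figures.** The plan states no figure on this point. Its only related figures, the precision statements in SAP 6.3, reproduce as p + 1.96 × √(p(1 − p)/n) with p = 0.01. For n = 100 this is 0.01 + 0.0195 = 2.95% (stated 3%); for n = 300 it is 0.01 + 0.0113 = 2.13% (stated 2.1%). The point does not depend on them.

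**6. Illustration with assumed rates.** N = 609 enrolled (SAP 2.5). The counts are 609 × 0.005 ≈ 3, × 0.01 ≈ 6, × 0.02 ≈ 12 and × 0.05 ≈ 30. Upper limits are exact two-sided 95% limits, the 0.975 quantile of Beta(x + 1, N − x). The two groups are taken as not overlapping.

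| Discontinued for a TEAE | Interrupted or reduced, stayed | Planned count (upper limit) | Either (upper limit) |
|---|---|---|---|
| 0 | 3 | 0/609 = 0% (0.6%) | 3/609 = 0.5% (1.4%) |
| 0 | 30 | 0/609 = 0% (0.6%) | 30/609 = 4.9% (7.0%) |
| 6 | 12 | 6/609 = 1.0% (2.1%) | 18/609 = 3.0% (4.6%) |
| 6 | 30 | 6/609 = 1.0% (2.1%) | 36/609 = 5.9% (8.1%) |

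The proper denominator is the Safety set. It may be smaller than 609, because subjects with a clear face and no truncal area to treat are not given cream at Visit 4-LTF.

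**The case against.** The strongest reply is that nothing is lost. Every TEAE is counted and listed, an LSR that needs withholding enters the same tables as an AE, and LSRs are tabulated by type, severity, visit and area. Dose-limiting TEAEs are not an endpoint in either document, protocol 17.3.1 asks only for AEs by relationship and severity, and no hypothesis is tested. On this view the request is for an extra table and no error has been shown.

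Much of that stands. A reader might infer that the SAP counts only TEAEs leading to discontinuation, so that intolerance goes unreported. The documents do not support that: the events are reported, and what is missing is the summary that marks them as dose-limiting. What survives is that the protocol collects the action taken and the SAP text summarises only an undefined part of it.

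Three further limits also stand.
- Protocol 14.1 defines action taken for the test article as a whole. No text shows that the AE form records face or trunk, or that a coded reason is kept for each stop.
- The table and listing shells (SAP section 10) are not in the text available, so a row or reason column there cannot be ruled out.
- Protocol 14.1 reports that in earlier use no subject stopped treatment because of the listed LSRs and that only two AEs, both mild and in one subject, were judged related. Section 2 puts that experience at up to 12 weeks. It gives no interruption rate, but it offers no support for a high one.

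**Conclusion.** The point holds as a gap in summary reporting and a missing definition. In the SAP text, TEAEs that led to interruption or dose reduction in subjects who stayed on study appear in no summary as dose-limiting, and discontinuation is open to more than one reading.

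The size cannot be derived from the documents. The 3 to 30 subjects rest wholly on an assumed 0.5% to 5% and on enrolment as the denominator. A reader might infer that a material share of subjects had to withhold the cream; nothing in the documents shows this. The conclusion also assumes that subjects can stay on study after an AE-related stop, which is inferred, and that the unseen shells do not already contain the row.

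Sample size, precision statements and clinical rules are unaffected.

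**What to change.** - In SAP 7.9.2, define discontinuation for AE purposes, stating whether it means withdrawal from the study or permanent stop of the test article.
- In Table 14.3.1.1, add the number and percentage of Safety-set subjects, and the number of events, with TEAEs whose recorded action was Drug Interrupted or Dose Reduced. Show Drug Withdrawn alongside if the existing count, once defined, does not cover it.
- If the CRF records treatment area and reason for each stop, add to SAP 7.8.3 a frequency table of stops and restarts by area and reason. If it does not, leave this out.

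The first two changes need a few lines of SAP text and one more descriptive row, from data that protocol 14.1 already requires. The third depends on the CRF. The downside is that the tolerability figure may look less favourable.
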